4. INVESTIGATIONAL PLAN

4.1. Overall Study Design

This is a Phase 2, open-label study designed to evaluate the safety and efficacy of 2 INCB050465 treatment regimens in subjects diagnosed with relapsed or refractory MZL (see [Figure 1](#)). A total of approximately 90 subjects will be enrolled.

Subjects with MZL that is relapsed or refractory to at least 1 line of prior systemic therapy that included an anti-CD20 antibody will be screened for eligibility. The study was originally planned to enroll 2 cohorts:

- Cohort 1: Subjects who have received prior ibrutinib (n = 60)
- Cohort 2: Subjects who have not received a prior BTK inhibitor (n = 60)

However, given the limited availability of ibrutinib (approved for MZL in the United States only), the number of subjects with relapsed or refractory MZL previously treated with ibrutinib is low. At the time of Protocol Amendment (Version) 3, only 2 subjects have been enrolled into Cohort 1, 18 months after the study start in JUN 2017. Therefore, Cohort 1 was closed to further enrollment for feasibility reasons.

Subjects already enrolled into Cohort 1 will continue to receive study treatment per the Protocol, and their data will be reported and analyzed separately from subjects in Cohort 2.

The first 60 subjects in Cohort 2 and any subjects enrolled in Cohort 1 who meet the eligibility criteria will be further allocated to 1 of 2 study treatment regimens through the IWRS (see [Section 5.1](#)):

- Treatment A: INCB050465 20 mg QD PO for 8 weeks followed by 20 mg once weekly PO.
 - Subjects in Cohort 1 receiving Treatment A will be referred to as Cohort 1A.
 - Subjects in Cohort 2 receiving Treatment A will be referred to as Cohort 2A.
- Treatment B: INCB050465 20 mg QD PO for 8 weeks followed by 2.5 mg QD PO.
 - Subjects in Cohort 1 receiving Treatment B will be referred to as Cohort 1B.
 - Subjects in Cohort 2 receiving Treatment B will be referred to as Cohort 2B.

To better understand the safety and efficacy of INCB050465, an additional 30 subjects will be enrolled into one of the two treatment regimens (A or B) being evaluated in this Study. The treatment regimen will be selected after enrollment is completed for Cohort 2 (ie, 60 subjects enrolled) and after evaluation of emerging safety and efficacy data from this and other

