monotherapy studies of INCB050465 in NHL. Once a treatment regimen is selected, the non-selected treatment regimen will be closed to further enrollment. Subjects receiving the non-selected treatment regimen may switch to the selected treatment regimen or remain on their current treatment regimen, provided the subject has not met study-treatment withdrawal criteria and there are no safety concerns for their current treatment regimen. There will be no re-baselining for subjects who switch treatment regimens and all subjects will continue to follow the same assessment schedule.

NOTE: The primary, secondary, [REDACTED] objectives and endpoints described in Section 2 are applicable for both cohorts; however, the cohorts will be analyzed separately, when applicable, as detailed in Section 9.

[figure not shown]
Subjects will receive treatment until disease progression, death, unacceptable toxicity, or consent withdrawal.

Subjects will be monitored for safety and efficacy periodically until disease progression, death, unacceptable toxicity, or withdrawal of informed consent. An IDMC will review safety data periodically as stated in the IDMC charter. Subjects will be evaluated for ORR by an IRC and followed for DOR, PFS, and OS.

An interim futility analysis is planned for Cohort 2 when 30 subjects have been treated and have been evaluated for response or have permanently discontinued study treatment because of disease progression, withdrawal of consent, or death. Cohort 2 will be terminated for futility if ≤ 10 of the 30 subjects responded (ie, CR or PR) based on assessments provided by the IRC. A timely assessment of response will be performed to avoid the risk of overenrollment.

After treatment discontinuation, subjects will be followed for safety and survival. Subjects who have discontinued study treatment due to reasons other than disease progression will be followed for either radiologic disease progression, the start of a new anticancer therapy, or death, whichever comes first. It is expected that the final analysis will occur no later than 2 years after the first dose of INCB050465 is administered to the last subject treated.

Figure 1: Study Design of INCB 50465-204

BTKi = Bruton's tyrosine kinase inhibitor; EOT = end of treatment; MZL = marginal zone lymphoma; QD = once daily

^a A futility analysis will be performed for Cohort 2 when the first 30 patients have been treated and evaluated for response (see Section 9.6).

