9.4.1.3. Other Efficacy Analyses

Analyses of ORR, DOR, CRR, and PFS as reported by the investigator will be summarized as described above.

Analyses of ORR, DOR, CRR, PFS as determined by IRC, and OS will also be summarized by treatment regimens (A or B) within each cohort.

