### **5.2. Treatment Groups**

This is a Phase 2, open-label study. All analyses will be conducted independently for Cohort 1 and Cohort 2, and there will not be multiplicity adjustment between the cohorts. Within each cohort, there will not be any statistical comparison between the treatment groups.

For the purpose of analysis, the 20 mg QW dosing period in Treatment A and the 2.5 mg QD dosing period in Treatment B are considered maintenance dosing periods. Within each cohort, data will be presented in summary tables by actual received treatment regimen and combined, with an exception for participants who cross over to the selected treatment regimen after the start of the maintenance dosing period.

For participants who cross over from the initially assigned treatment regimen to the selected treatment regimen, if the crossover happens before/on the start of the maintenance dosing period, then the participant will be summarized, according to the actual received treatment, in the selected treatment regimen; otherwise, the participant will be summarized in:

- A separate treatment regimen (ie, Crossover) for the safety summaries during the maintenance dosing period (eg. summaries of TEAEs and exposure).
- The initially assigned treatment regimen for all other summaries.

Per Protocol Amendment (Version) 3, Cohort 1 was closed to further enrollment. If the number of participants who have enrolled in Cohort 1 is relatively few, summary tables will be replaced with listings.

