### 9.2.3. Adverse Event Summaries

Overall summaries of TEAEs by treatment regimen will be provided during the INCB050465 initial QD dosing period, maintenance dosing period, and overall period (ie. all TEAEs regardless of the timing of occurrence). These summaries will include the following:

- Number (%) of participants reporting any TEAEs
- Number (%) of participants reporting any Grade 3 or higher TEAEs
- Number (%) of participants reporting any serious TEAEs
- Number (%) of participants reporting any TEAEs related to INCB050465
- Number (%) of participants reporting any Grade 3 or higher TEAEs related to INCB050465
- Number (%) of participants reporting any serious TEAEs related to INCB050465

- Number (%) of participants who had TEAE with fatal outcome
- Number (%) of participants with INCB050465 dose reductions because of TEAEs
- Number (%) of participants who temporarily interrupted INCB050465 because of TEAEs
- Number (%) of participants who permanently discontinued INCB050465 because of TEAEs

The following summaries will be produced for TEAEs during the overall period by MedDRA term (if 10 or fewer participants appear in a table, a listing may be appropriate):

- Summary of TEAEs by SOC and PT
- Summary of TEAEs by PT in decreasing order of frequency
- Summary of TEAEs by SOC, PT, and maximum severity
- Summary of TEAEs by PT and maximum severity in decreasing order of frequency
- Summary of Grade 3 or higher TEAEs by SOC and PT
- Summary of Grade 3 or higher TEAEs by PT in decreasing order of frequency
- Summary of serious TEAEs by SOC and PT
- Summary of serious TEAEs by PT in descending order of frequency
- Summary of INCB050465 treatment-related TEAEs by SOC and PT
- Summary of INCB050465 treatment-related TEAEs by PT in decreasing order of frequency
- Summary of INCB050465 treatment-related TEAEs by SOC, PT, and maximum severity
- Summary of Grade 3 or higher INCB050465 treatment-related TEAEs by SOC and PT
- Summary of INCB050465 treatment-related serious TEAEs by SOC and PT
- Summary of TEAEs with a fatal outcome by SOC and PT
- Summary of TEAEs leading to INCB050465 dose reduction by SOC and PT
- Summary of TEAEs leading to INCB050465 dose interruption by SOC and PT
- Summary of TEAEs leading to discontinuation of INCB050465 by SOC and PT
- Summary of selected TEAEs of special interest by maximum severity

- Summary of time to onset of selected TEAEs of special interest

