### Amendment 1 (27 AUG 2020)

- Section 4.1.4 was updated to include details of rules for handling partial/missing onset or end date of TEAEs in the calculation of time to onset or duration of a TEAE. Rules for partial/missing date of last dose were updated to include details of handling situations where both month and day are missing.
- Section 5.2 was modified to provide details regarding how crossover participants will be summarized.
- Section 5.3 was updated to remove the efficacy evaluable analysis set and use the FAS for all analyses on efficacy data. This change is to comply with comments from FDA that any participants who received at least 1 dose should be included in the efficacy analyses for a single-arm trial. The all-screened population was added for the summary of analysis populations.
- Section 6.1.2 was modified to remove summaries of tumor markers but only keep listings. Relapsed/refractory status to the most recent prior therapy was added to the summary table of disease history because the response to last regimen before entering the study may be a prognostic factor for clinical outcomes.
- Section 6.2 was modified to add summaries of participants who are ongoing with treatment or still in the study.
- Section 6.4 was modified to change the calculations of duration of treatment and average dose during the maintenance dosing period because Group B with 2.5 mg QD was selected as the maintenance dose.
- Section 7.3 and Section 7.4 were modified to add efficacy analyses for participants in the FAS who have at least 2 prior therapies to support an indolent NHL indication in the same line of therapy as with follicular lymphoma in Study INCB 50465-203.
- Section 7.3.1 was modified to replace the efficacy evaluable analysis set with the FAS. This change is to align with Protocol Amendment 4 dated 23 DEC 2019 and include all treated participants in the efficacy analyses to comply with comments from FDA.
- Section 7.3.2 was modified to add "unknown" as a category for bone marrow involvement at baseline. Relapsed/refractory status to the most recent prior therapy was added to the subgroup analysis because the response to last regimen before entering the study may be a prognostic factor for clinical outcomes.
- Section 7.4.3 was modified to update references of censoring for PFS.

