- Section 9.2.2 was updated to include details of analyses on time to onset of selected TEAEs of special interest. Summaries of longest duration of selected TEAEs of special interest were added to have a better understanding of the safety profile in terms of duration of class-effect AEs as well as AEs influenced by treatment regimens. "Grade 2 or higher" was changed to "Grade 3 or higher" for time to onset summary of rash. This change was made to be consistent with other PI3K inhibitors, which highlighted more severe cutaneous reactions graded as Grade 3 or higher in the labeling. "Herpes simplex virus infection" was changed to "herpes simplex" based on MedDRA coding dictionary

as a broader term. Exfoliative dermatitis was added to the list of TEAEs of special interest.

- Section 9.2.3 was updated to include summary of TEAEs by PT and maximum severity in decreasing order of frequency, summary of longest duration of selected TEAEs of special interest, and additional supporting summaries during the INCB050465 initial QD dosing period and the maintenance dosing period, which will provide supportive data of the safety profile of the maintenance dose. Summary of nonserious of TEAEs by SOC and PT was removed because it will not be used for the clinical study report but will be provided for result disclosure.
- Section 9.3.2 was modified to include ALT and AST in the line graphs as additional supportive analyses for laboratory events of special interest.
- Section 9.3.3 was added to identify potential Hy's law events to better monitor liver toxicity.
- Section 9.3.4 was updated to align with the analysis plan for adverse events of special interest. Summary of worsening of laboratory events of special interest was removed because this is covered by the summary of worsening of laboratory abnormalities.
- Section 9.5 was updated to change the high threshold of QTcF and QTcB interval from 460 to 450 milliseconds for purpose of analysis. This change is to comply with the categories outlined in FDA Guidance for Industry (E14 Clinical Evaluation of QT/QTc Interval Prolongation and Proarrhythmic Potential for Non-Antiarrhythmic Drugs) used to characterize outliers in QTc values.

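### Column B mixes original and later-enrolled subjects: does the SAP need a separate table of the first 60 in Cohort 2?

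*SAP*

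**What the plan says.** Protocol section 4.1 states that the first 60 subjects of Cohort 2 "will be further allocated to 1 of 2 study treatment regimens through the IWRS". After those 60 are enrolled, one regimen is chosen, "the non-selected treatment regimen will be closed to further enrollment", and 30 further subjects enter the chosen one. The Amendment 1 entry in SAP section 11.2 shows which it was: a calculation was changed "because Group B with 2.5 mg QD was selected as the maintenance dose".

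SAP section 5.2 states that, within each cohort, "data will be presented in summary tables by actual received treatment regimen and combined", with rules for subjects who switch:

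- A switch by the start of maintenance: "the participant will be summarized, according to the actual received treatment, in the selected treatment regimen".
- A later switch: a separate Crossover group in maintenance-period safety summaries, and the originally assigned regimen everywhere else.

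Protocol section 9.4 pools A and B for primary and secondary efficacy. Under Protocol section 9.4.1.3, IRC-assessed response endpoints, PFS and OS "will also be summarized by treatment regimens (A or B) within each cohort". SAP section 9.2.3 gives by-regimen TEAE counts for the initial period, the maintenance period and overall, including "Number (%) of participants who permanently discontinued INCB050465 because of TEAEs". SAP sections 3.2 and 5.2 rule out any statistical comparison of the regimens.

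Neither the subgroup list in SAP section 7.3.2 nor any Appendix A title separates the first 60 from the added 30. Table shells are in a separate document and part of the SAP is redacted, so this absence is established for the public text only.

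**The concern.** Column A holds only subjects from the first 60. Column B holds its share of those plus 30 who started later and, at a common data cutoff, have been observed for less time. A crude percentage with an event rises with time at risk, so column B could show fewer AE discontinuations than A even if the regimens were identical. The selected regimen would look slightly better tolerated for a reason unrelated to dose.

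The setting makes this worth checking. The columns sit side by side, and Amendment 1 says of the added period summaries that they are ones "which will provide supportive data of the safety profile of the maintenance dose". Time-to-onset methods cover only the listed AEs of special interest, and none is described for AE discontinuation. The SAP gives switchers their own displays because they blur the reading of the non-selected regimen, but gives the added 30 no similar display. The obvious remedy would be a table of the first 60 by assigned regimen.

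**Working it through.** The plan gives no figure for this effect, so there is none to reproduce. The check sizes the gap that unequal follow-up alone would create.

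**Cause.** The mixing arises because all 30 added subjects are enrolled into B. Grouping by assigned regimen would mix them in just the same.

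**Share of column B.** Share = 30/(nB + 30), where nB is the number of the first 60 allocated to B. The ratio is not stated. For nB = 30 the share is 30/60 = 50%; for nB = 40, 43%; for nB = 20, 60%.

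**Follow-up.** Protocol section 4.5 expects about 2 years to accrue 90 subjects. Assumed uniform, that is 90/24 = 3.75 per month: the first 60 enter in months 0–16 and the last 30 in months 16–24. Two cutoffs:

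- Month 38: 14 months after the last first dose, being the 12 months from response in SAP section 7.3 plus an assumed 2 months to respond. Follow-up is 22–38 months (mean 30) for the first 60 and 14–22 (mean 18) for the last 30.
- Month 48: the latest final analysis. Means are 40 and 28 months.

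**Crude AE discontinuation.** Let h be the monthly AE-discontinuation hazard, g the hazard of stopping for other reasons, and k = h + g, the same in A and B. Averaged over follow-up uniform on (a, b):

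incidence = (h/k) × [1 − (e^(−ka) − e^(−kb)) / (k(b − a))]

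The Protocol synopsis expects about 52 weeks of treatment, so k = 1/12. For h = 0.02 at month 38:

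- First 60: 0.24 × [1 − (0.1599 − 0.0421)/1.333] = 21.9%.
- Last 30: 0.24 × [1 − (0.3114 − 0.1599)/0.667] = 18.5%.
- Column B, 30:30 split: the average, 20.2%. Gap 1.7 points.

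SE of the A−B difference = √[pA(1 − pA)/30 + pB(1 − pB)/60].

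| Cutoff | h per month | A | B | Gap (points) | SE (points) |
|---|---|---|---|---|---|
| 38 | 0.01 | 10.9% | 10.1% | 0.8 | 6.9 |
| 38 | 0.02 | 21.9% | 20.2% | 1.7 | 9.2 |
| 38 | 0.03 | 32.8% | 30.3% | 2.5 | 10.4 |
| 48 | 0.01 | 11.5% | 11.2% | 0.4 | 7.1 |
| 48 | 0.02 | 23.1% | 22.4% | 0.7 | 9.4 |
| 48 | 0.03 | 34.6% | 33.5% | 1.1 | 10.6 |

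For A:B splits from 20:40 to 40:20 the gaps are 0.7–3.0 points at month 38 and 0.3–1.3 at month 48.

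**Stress cases** (h = 0.03, month 38). Mean treatment of 20 months, 30:30: A 46.3%, B 40.8%, gap 5.4 (unrounded). Mean treatment of 33 months, which leaves almost no stopping for any other reason: first 60 58.7%, last 30 41.5%, B 50.1%, gap 8.6, SE 11.1. The same with a 40:20 split: B = (20 × 58.7 + 30 × 41.5)/50 = 48.4%, gap 10.3, SE 10.5.

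**Early switchers.** At 3.75 per month, 8 weeks (1.84 months) holds 6.9 subjects. With half in A, 3 to 4 at most could move to column B under the early-switch rule.

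**Would a first-60 table help?** At month 38 everyone has at least 14 months of potential follow-up. Counting events only to 14 months gives (h/k)(1 − e^(−14/12)) = 8.3%, 16.5% and 24.8% in both groups: gap zero with all 90 subjects kept. The common window removes the artefact; the restriction does not do so by design. Restriction also costs precision. For h = 0.01, 0.02 and 0.03, the planned 30-versus-60 reading has root mean square error √(SE² + gap²) = 7.0, 9.3 and 10.7 points, against an SE of √[2pA(1 − pA)/30] = 8.1, 10.7 and 12.1 for 30 versus 30. In the 20-month case it is 12.3 against 12.9. Only in the 33-month extreme does the order reverse (14.0 against 12.7).

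**The case for a change.** The best case for a change is that it is cheap and the columns will be compared whatever the SAP says. The first 60 are the only subjects allocated to A and B concurrently, and B was chosen using emerging data that included this study's. Two descriptive tables need no patients or visits. Appendix A of the SAP lets the output list change without an amendment, provided the nature of the analysis is unaffected.

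The description stands: column B is half later entrants under an even split, and the crude percentages are not equally followed. The rest carries less weight:

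- **Nothing inferential depends on the columns.** The primary ORR pools A and B and waits for about 12 months of follow-up from first response in all responders. DOR, PFS and OS use Kaplan–Meier estimates, which allow for unequal follow-up. The initial 8-week period is complete for early and late entrants alike by either cutoff.
- **The analogy with switchers is weak.** A late switcher received two maintenance regimens. An added subject was enrolled into one.
- **The reader can see the difference.** SAP section 6.4 shows treatment duration by period, section 9.2.2 gives life-table onset for the listed events, and Appendix A lists disposition, dosing and events leading to discontinuation. An analyst who wants a common time window has the data for it.
- **The Appendix A allowance is limited.** It covers the output list, not new text in SAP sections 7.3.1 or 9.2.3.

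A related remark is that Protocol section 5.1.2 and SAP section 3.1 treat randomization as not applicable and state no allocation method. That is missing detail: assignment is central, follows confirmation of eligibility, and Protocol section 5.1.1 refers to an IWRS Manual.

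**Conclusion.** No change is needed. Column B does pool original and later subjects, as it must once 30 people are added to one regimen. The resulting distortion of crude AE-discontinuation percentages is about 0.4 to 2.5 points under a 30:30 split, uniform accrual, equal constant hazards and 12 months' mean treatment. It stays below one standard error even at 8.6 points (33 months' mean treatment, 3% per month) or 10.3 points (the same with a 40:20 split, where the margin is slim). The direction favours B under these assumptions; unequal or changing hazards could alter it. The split and hazards are assumptions, not figures from the documents.

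The plan makes no claim about A against B, and the pooled efficacy results do not depend on the split. A first-60 table would be an extra description that changes no conclusion and, outside the extreme case, is noisier than the columns already planned. Reading the two columns with the exposure summaries beside them is enough.

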## 6.4. Exposure

For participants in the safety population, exposure to INCB050465 will be summarized descriptively as the following:

- **Duration of treatment (days):** Date of last dose – date of first dose + 1.
- **Duration of treatment during the initial QD dosing period (days):** Date of last dose during the initial QD dosing period – date of first dose + 1.
- **Duration of treatment during the maintenance dosing period (days):** Date of last dose – date of first dose during the maintenance dosing period + 1. Crossover participants who switched to the selected treatment regimen after the start of the maintenance dosing period will be summarized in a separate group (ie, Crossover).
- **Average reported daily dose during the initial QD dosing period (mg/day):** total reported dose taken during the initial QD dosing period (mg) / duration of treatment during the initial QD dosing period (days).
- **Average reported daily dose during the maintenance dosing period (mg/day):** total reported dose taken during the maintenance dosing period (mg) / duration of treatment during the maintenance dosing period (days). Crossover participants who switched to the selected treatment regimen after the start of the maintenance dosing period will be summarized in a separate group (ie, Crossover).
- **Dose modifications:** Number of participants who had dose reduction and interruption will be summarized. The number of dose reductions and the number of interruptions for each participant will be summarized.

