### 9.2.2. Adverse Events of Special Interest

The number of participants who experienced any TEAEs of special interest listed below will be tabulated by maximum severity.

- Colitis
- Diarrhea
- Exfoliative dermatitis
- Febrile neutropenia
- Intestinal perforation
- Rash
- Pneumonitis
- Pneumonia
- PJP infection
- CMV infection
- Herpes simplex
- Varicella zoster virus infection

The time to onset of a TEAE is defined as the interval between the date of first dose of study drug and the date of the first occurrence of a TEAE. Participants who have not experienced a TEAE at the time of analysis will be right-censored at the earlier of 30 days after the last dose date and date of last study visit through the end of safety follow-up. If participants have missing or partial last dose dates of study drug or onset date of a TEAE, the partial or missing dates will be handled using the rules explained in Section 4.1.4.

Summaries of time to onset of new or worsening Grade 3 or higher AEs will be provided using descriptive statistics and the life-table method for rash, colitis, diarrhea, febrile neutropenia, pneumonia, herpes simplex, and varicella zoster virus infection. In addition, summaries of time to onset of new or worsening AEs of any grade will be provided using descriptive statistics and the life-table method for colitis, diarrhea, exfoliative dermatitis, intestinal perforation, pneumonia, pneumonitis, PJP infection, CMV infection, herpes simplex, and varicella zoster virus infection. Kaplan-Meier plots of time to onset of new or worsening Grade 3 or higher AEs will be provided for rash, colitis, and diarrhea. In addition, Kaplan-Meier plots of time to onset of new or worsening AEs of any grade will be provided for colitis and diarrhea.

Descriptive statistics of time to onset of these TEAEs of special interest are based on all participants who have experienced a TEAE at the time of analysis. To summarize these TEAEs of special interest using the life-table method, the effective sample size is defined as the number of participants at the beginning of interval minus half the participants censored in the interval. The conditional proportion is calculated as the number of first events divided by the effective sample size in the interval.

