- Summary of time to onset of selected TEAEs of special interest: life-table method
- Summary of longest duration of selected TEAEs of special interest

The following supporting summaries will be produced for TEAEs during the INCB050465 initial QD dosing period and the maintenance dosing period by MedDRA term. For the supporting summaries during the maintenance dosing period, participants who cross over to the selected treatment regimen after the start of the maintenance dosing period will be summarized in a separate group (ie, Crossover).

- Summary of TEAEs by PT in decreasing order of frequency
- Summary of TEAEs by PT and maximum severity in decreasing order of frequency
- Summary of Grade 3 or higher TEAEs by PT in decreasing order of frequency
- Summary of serious TEAEs by PT in descending order of frequency
- Summary of TEAEs with a fatal outcome by SOC and PT
- Summary of TEAEs leading to discontinuation of INCB050465 by SOC and PT

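### Safety tables place late A-to-B switchers as whole participants: none is cut at the switch, and the maintenance-period AE-discontinuation figure for Treatment A runs high

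*SAP*

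**What the plan says.** SAP 5.2 defines maintenance as the 20 mg once-weekly (QW) period of Treatment A and the 2.5 mg daily (QD) period of Treatment B. A participant who crosses to the selected regimen at or before the start of maintenance is counted under that regimen. One who crosses later goes to "A separate treatment regimen (ie, Crossover) for the safety summaries during the maintenance dosing period" and to "The initially assigned treatment regimen for all other summaries". SAP 11.2 (Amendment 1) records that B was selected, so late switchers go from A to B.

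Other sections apply this rule:

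- **Exposure (SAP 6.4).** Maintenance duration is the date of last dose minus "date of first dose during the maintenance dosing period + 1". For late switchers: "Crossover participants who switched to the selected treatment regimen after the start of the maintenance dosing period will be summarized in a separate group".
- **TEAEs (SAP 9.2.3).** The by-regimen overviews of treatment-emergent AEs "will be provided during the INCB050465 initial QD dosing period, maintenance dosing period, and overall period". The detailed tables are introduced by "The following summaries will be produced for TEAEs during the overall period by MedDRA term" and have no Crossover group. For the supporting maintenance tables, "participants who cross over to the selected treatment regimen after the start of the maintenance dosing period will be summarized in a separate group".
- **Time to onset (SAP 9.2.2, 9.3.4).** Participants without an AE of special interest (AESI) "will be right-censored at the earlier of 30 days after the last dose date" or at the last study visit through safety follow-up. Laboratory events are censored at the last graded visit. Neither rule mentions the switch.
- **Efficacy (SAP 7.3.1, 7.4.1 to 7.4.3).** Sensitivity analyses show switchers as a separate group for ORR and CRR, and cut DOR and PFS at the switch.

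**The concern.** A late switcher has two stretches of maintenance, the first on 20 mg QW and the second on 2.5 mg QD. The safety tables put both in one column, and which column depends on the table.

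In the maintenance tables this is also selective. SAP 3 allows a switch only if withdrawal criteria have not been met, so a switcher is by definition someone who had not stopped. Column A keeps those who stopped before they could switch, were ineligible or chose to stay. It loses those who did well enough to switch.

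Protocol 1.4 proposes the weekly schedule because it may lower the frequency of AEs that lead to withdrawal. Protocol 5.4.4 says most immune-related AEs arise after the first 9 weeks, which is in maintenance. A reader who wants to know how 20 mg QW was tolerated would look at the maintenance A column.

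**Working it through.** The plan states no figure on this point, so there is none to reproduce. The check is textual, followed by an illustration on assumed inputs.

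**1. Where the data go**

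| Data | Maintenance-period tables | Overall-period tables |
|---|---|---|
| Late switcher, 20 mg QW before the switch | Crossover | A |
| Late switcher, 2.5 mg QD after the switch | Crossover | A |
| A participant who stops for an AE before any switch | A | A |

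The first row shows 20 mg QW data leaving A. The second shows 2.5 mg QD data entering A.

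**2. Direction.** Let N be the A participants entering maintenance, S the late switchers and D the AE stops on 20 mg QW before any switch. No switcher contributes to D, so maintenance column A shows D/(N − S): all the stops, fewer people.

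**3. One worked scenario (all inputs assumed).** Uniform accrual over 18 months; maintenance from month 2 of treatment; selection 3 months after accrual ends; cutoff 24 months after accrual ends; AE-stop and other-stop hazards 0.02 per month each on either schedule; 75% of those on treatment at selection switch. Time from maintenance start is then uniform on 1-19 months to selection and on 22-40 months to cutoff.

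- On treatment at selection: (e^−0.04 − e^−0.76)/(0.04 × 18) = (0.9608 − 0.4677)/0.72 = 0.685. So S/N = 0.75 × 0.685 = 51.4%.
- On treatment at cutoff: (e^−0.88 − e^−1.60)/0.72 = (0.4148 − 0.2019)/0.72 = 0.296.
- AE stop by cutoff if nobody switched: 0.5 × (1 − 0.296) = 35.2%.
- AE stop before selection: 0.5 × (1 − 0.685) = 15.8%.
- D/N = 0.75 × 15.8% + 0.25 × 35.2% = 20.6%.
- Column A as planned: 20.6/(100 − 51.4) = 42.4%, which is 1.20 times 35.2%.
- A and Crossover added together: 35.2%, because this scenario has no schedule effect.

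Per unit of exposure, all A entrants spend 0.206/0.02 = 10.31 months each on 20 mg QW. The switchers' share of that is 0.75 × (1/18) × ∫ t e^(−0.04t) dt from 1 to 19, or 0.75 × 6.12 = 4.59 months, and it leaves A. Column A keeps 5.72 months and shows 0.206/5.72 = 0.036 per month, 1.80 times the true 0.020. Splitting at the switch restores 0.206/10.31 = 0.020.

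**4. Range.** Varying accrual (12, 18, 24 months), selection lag (0, 3, 6 months) and each hazard (0.02, 0.04), with no schedule effect:

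| Uptake | Column A % ÷ no-switch % | Column A rate ÷ 20 mg QW rate |
|---|---|---|
| 50-75% | 1.02 to about 1.23 | 1.19 to 1.89 |
| 10-25% | about 1.05 at most | 1.02 to 1.13 |

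**5. Overall-period tables.** Assume 30 participants in A, 30% with a given event before any switch, m late switchers, and a fraction q of the event-free switchers having a first event after the switch. Column A then shows (9 + 0.7qm)/30. With q = 10% to 30% this is 31.2% to 33.5% for m = 5 and 33.5% to 40.5% for m = 15. The excess over 30% is events that began on 2.5 mg QD.

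**6. Average dose does not reveal the mix.** 20 mg QW is 20/7 = 2.86 mg/day, against 2.5 mg/day. A Crossover group with 25% to 75% of its maintenance time before the switch would show 2.59 to 2.77 mg/day.

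**The case against.** The rule is disclosed and the Crossover column is labelled. Counting switchers under initial assignment in overall tables is a recognisable convention. SAP 3.2 and 5.2 plan no comparison between regimens. The combined and maintenance B columns are unaffected, and SAP 11.2 says the period tables support the selected maintenance dose, which is B. Adding A and Crossover recovers the percentage for all A entrants. Dosing and AE listings (2.5.2, 2.7.1, 2.7.6) would let the sponsor rebuild any split. A split also has faults of its own: SAP 9.2.1 counts AEs up to 30 days after the last dose, so events soon after a switch may belong to the earlier schedule, and switchers are survivors.

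All of this stands as a limit on importance. None of it supplies a planned table of switchers' non-terminal TEAEs or exposure before versus after the switch.

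A reader might infer that the SAP protects efficacy properly and leaves only safety exposed. That goes too far: the ORR and CRR sensitivity analyses also use a whole-participant Crossover group, and only DOR and PFS are cut at the switch. A reader might also infer that the choice of B is in doubt. The documents do not support that either: B had been selected by SAP Amendment 1, and Protocol 1.4 gives the same fewer-withdrawals rationale for 2.5 mg QD.

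**Conclusion.** The point holds as a minor one about reporting of the non-selected regimen. That the maintenance A column overstates AE discontinuation relative to all A entrants, and that overall tables count post-switch events under A, follow from the SAP text. How far cannot be derived, because the documents give neither the number of switchers nor the AE-stop rate. The ranges above rest on assumed constant hazards, assumed timing and no schedule effect. At low uptake the distortion is small.

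A reader might take D/N as the correct value and conclude that column A is inflated by 1/(1 − S/N), for example twofold if half of A switches. That is not supported. D/N treats switchers' 20 mg QW follow-up, which ended at the switch, as event-free, so it is biased low. In the worked scenario it is 20.6% against a no-switch 35.2% (0.59 times), further off than column A's 42.4%. At 50-75% uptake it is 0.46 to 0.87 of the no-switch proportion, and it was further off than column A in every scenario run.

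**What to change.** Keep the planned tables and add, by amendment to SAP 5.2, 6.4, 9.2.2, 9.2.3 and 9.3.4:

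- Supplementary maintenance-period TEAE and exposure tables that count late switchers under A up to the switch date and under Crossover (post-switch) from that date, events by onset date. Make exposure-adjusted rates the main measure, because follow-up in A now ends at the switch.
- AESI and laboratory time-to-onset summaries censored at the switch, parallel to the DOR and PFS sensitivity analyses.
- Footnotes stating that a participant can appear in both columns, that switchers are survivors of earlier treatment, that events soon after the switch may reflect the earlier schedule, and how many participants outside A's own schedule were moved to QW under Protocol Table 5.

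Do not offer A plus Crossover as the denominator for AE discontinuation on 20 mg QW: that reproduces D/N.

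The cost is a few more tables from dates already collected. Protocol 8.1.2 records each change in severity as a separate AE, so worsening after the switch has its own date. The downsides are double appearance and the survivor effect: with no schedule effect, and an assumed frailty variance of 0.5 to 2 on the AE-stop hazard, post-switch AE-stop rates came out at 0.61 to 0.96 of the pre-switch rate. The split columns should not be read as A versus B.
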